Another more generic QOL tool, is the EuroQol generic health index, the EQ-5D-3L (<http://www.euroqol.org/home.html>). EQ-5D essentially consists of 2 pages - the EQ-5D-3L descriptive system and the EQ visual analogue scale (EQ VAS). The EQ-5D-3L descriptive system comprises the following 5 dimensions: mobility, self-care, usual activities, pain/discomfort and anxiety/depression. Each dimension has 3 levels: no problems, some problems, severe problems. The respondent is asked to indicate his/her health state by ticking (or placing a cross) in the box corresponding to the most appropriate statement in each of the 5 dimensions. The EQ VAS records the respondent's self-rated health on a vertical, visual analogue scale where the endpoints are labeled 'Best imaginable health state' and 'Worst imaginable health state'. This information can be used as a quantitative measure of health outcome as judged by the individual respondents.

We aim to define a HR-QOL during this trial that is more suitable for the evaluation of a treatment directed at short-term impact on health outcome. If a novel HIV specific HR-QOL measure is demonstrated to work well in our setting, it can be used in future clinical trials. In order to explain the differences in HR-QOL measures between patient groups it is important to link it with a symptom list. The best known and validated list is the HIV symptom index developed by Justice [56]. This 20-item self-completed symptom index assesses whether symptoms are present or absent and their severity on a 4-point scale (0 = "does not bother me at all" to 4 = "bothers me a lot"). However, the 20-item list does not contain symptoms that are targeted to patients with possible side effects of steroids, or with TB-IRIS specific symptoms.

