21.2. Methodology

Measures and their adaptation

1. Existing and validated HR-QOL measures will be used as originally designed: **PROQOL-HIV and EQ-5D-3L**, in combination with **Karnofsky score** and an adapted **HIV-symptom index**. As far as possible the tools will be self-administered by the patient. In case the patient is illiterate a trained study counsellor will read the questions to them. A brief review for completeness by the site investigators will be done. The PROQOL-HIV will be adapted by asking specifically for HIV and TB-related symptoms. The number of questions will not change, but for example the sentence "I have been satisfied with my HIV medicine" would become "I have been satisfied with my HIV and TB medicines".
2. The 20-item HIV symptom index will be complemented with symptoms targeted to patients with IRIS and side effects of steroids. This will be prepared by the investigators and presented and discussed with experts in TB-IRIS from the INSHI network before implementation.
3. The tools (PROQOL-HIV, EQ-5D and HIV symptom index) will be translated in Xhosa. This will include two forward translations and one reconciled version: one backward translation of the reconciled version. For the PROQOL-HIV a Zulu translation is already available, which will be used to facilitate the translation process, as these two language share similarities.
4. Initial validation of the comprehensiveness and the comprehensibility (cognitive interview) will be performed on a sample of 10 patients (including at least 5 with TB-IRIS). At the end of the surveys open-ended questions will be asked such as:
 - a. Did you have trouble understanding what we meant by any of the symptoms (items) listed? If so, please list them and explain why it was confusing to you.
 - b. Do you think that these symptoms are the most common and the most bothersome for patients with TB-HIV who start ART?
 - c. Are there any other symptoms that you have found particularly bothersome? If so, please describe the symptom and how much it has bothered you.
 - d. Are there any other symptoms that you hear about that bother people you know who have TB and HIV? Please describe the symptom and how much it seems to bother them.

These patients will be personally debriefed by trained interviewers, to make sure that the written responses as documented at the end of the survey accurately represent their impressions.

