- p) Comparison of quality of life assessment between the two arms at week 4 and at week 12. In the trial, the following measurements were performed: PROQOL-HIV, EQ-5D-3L, HIV symptom index and Karnofsky score. For EQ-5D-EL we will compare the proportion of patients in the different domain levels using the Chi-square test, and we will compare the means of the VAS score using the t-test or Wilcoxon rank sum test as appropriate. For the adapted ProQOL HIV the summary score per domain (adapted from [1]) will be compared using the t-test

or Wilcoxon rank sum test as appropriate. For the HIV-symptom index the frequency (proportion) and the severity of each symptom (score 1-2 vs score 3-4) will be compared using the Chi-square test. Because of multiplicity, Bonferroni correction will be applied in the analysis of HIV symptoms. Karnofsky score will be compared using the t-test or Wilcoxon rank sum test as appropriate.

- q) The cumulative proportion of participants who develop adverse events ascribed to TB treatment, ART or co-trimoxazole requiring interruption of one or more of these medications (for > 5 days) within 12 weeks of randomisation will be compared using Chi-square test or Fisher exact test (as appropriate).
- r) The cumulative proportion of participants who develop drug rash or drug-induced liver injury ascribed to TB treatment, ART or co-trimoxazole and requiring interruption of one or more of these medications (for > 5 days) within 12 weeks of randomisation will be compared using Chi-square test or Fisher exact test (as appropriate).

5. Analysis of secondary safety and tolerability endpoints

A number of secondary safety and tolerability analyses will be performed, all using the all-patients-treated approach (this excludes those participants who were randomized but never started study medication and/or ART).

- a) Comparison of proportion of participants in each arm who develop at least one of the pre-specified potential corticosteroid-associated adverse events within 4 weeks and within 12 weeks of randomization using Chi-square test or Fisher exact test (as appropriate). The proportion of participants in each group who develop individual potential corticosteroid-associated adverse events within 4 weeks and within 12 weeks of randomization will also be compared.

The pre-specified potential corticosteroid-associated adverse events are:

- New hypertension > 160/100
- New poor BP control on treatment > 160/100

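### SAP 4(p) leaves score 0 out of the HIV-symptom severity comparison, so that test runs on a post-randomisation subset and can mislead if zeros differ by arm

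*Supplement*

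**What the plan says.** SAP section 4, item p, plans two comparisons per symptom, at week 4 and at week 12. It opens "For the HIV-symptom index the frequency (proportion) and the severity of each symptom" and gives the severity rule as "the severity of each symptom (score 1-2 vs score 3-4) will be compared using the Chi-square test". It adds: "Because of multiplicity, Bonferroni correction will be applied in the analysis of HIV symptoms". The divisor is not given. The SAP does not say which score counts towards frequency, where a 0 goes, or what the severity denominator is. The opening of section 4 places all its analyses on the ITT and all-patients-treated populations.

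Protocol v1.4 section 21.1 says the index "assesses whether symptoms are present or absent and their severity on a 4-point scale". The lowest anchor is 0, worded "does not bother me at all", and the highest is 4. Section 21.2 says "The 20-item HIV symptom index will be complemented with symptoms targeted to patients with IRIS and side effects of steroids". The number of added symptoms is not stated. The index is one of the four instruments in secondary efficacy endpoint 8 (protocol section 6.2).

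**The concern.** On the protocol's anchors, 0 is the best rating a participant can give, and the severity rule has no place for it. Anyone whose symptom has gone or no longer bothers them is left out of the severity test instead of being counted as a good result. What remains is defined by the week 4 or week 12 score itself, so it is formed after randomisation, and its size can differ by arm and by symptom.

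Unequal zeros are plausible here. The protocol hypothesises that prednisone lowers the incidence and severity of TB-IRIS (section 3.7) and cites faster symptom improvement on prednisone in the group's earlier treatment trial (section 3.3). For the added steroid side-effect symptoms the imbalance could run the other way: extra mild complaints on prednisone would enlarge its denominator and lower its severe percentage.

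Elsewhere the SAP says so when it narrows a denominator. Items h and m of section 4 state that only participants meeting the INSHI criteria are included. Item p has no such statement.

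**Working it through.** The plan states no figure for this analysis, so there is none to reproduce. The documents give no score distribution either. All splits below are assumptions chosen to show the range, including a case with no distortion.

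**Codes.** Integers from 0 to 4 make five codes, not four, so section 21.1 contradicts itself. The SAP split uses four of them (1, 2, 3, 4).

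**Formula.** Let z be the share scoring 0 and s the share scoring 3-4 among all respondents in an arm. The severity test as written compares s / (1 − z). The ratio of prednisone to placebo in that test is therefore

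(s_pred / s_plac) × (1 − z_plac) / (1 − z_pred).

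The second factor is the distortion. It equals 1 only when the share of zeros is the same in both arms.

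**Cases** (score 0 / 1-2 / 3-4). Cases 1 and 2 are in per cent. Cases A to C are counts with 120 per arm, from 240 randomised 1:1 and assuming that everyone responds.

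| Case | Placebo | Prednisone | 3-4 among all | 3-4 among scores 1-4 (as written) | Score ≥1 |
|---|---|---|---|---|---|
| 1 | 40/30/30 | 55/22.5/22.5 | 30% vs 22.5% | 50% vs 50% | 60% vs 45% |
| 2 | 40/30/30 | 55/17.5/27.5 | 30% vs 27.5% | 50% vs 61.1% | 60% vs 45% |
| A | 24/48/48 | 72/24/24 | 40% vs 20% | 50% vs 50% | 80% vs 40% |
| B | 24/56/40 | 84/12/24 | 33.3% vs 20% | 41.7% vs 66.7% | 80% vs 30% |
| C | 24/48/48 | 24/72/24 | 40% vs 20% | 50% vs 25% | 80% vs 80% |

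Checks with the formula:
- Case 1: (22.5/30) × (60/45) = 0.75 × 1.333 = 1.00.
- Case 2: (27.5/30) × (60/45) = 0.917 × 1.333 = 1.22.
- Case A: (20/40) × (80/40) = 0.5 × 2 = 1.00.
- Case B: (20/33.3) × (80/30) = 0.6 × 2.667 = 1.60.
- Case C: (20/40) × (80/80) = 0.50, no distortion.

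**Uncorrected chi-square p-values at 120 per arm:**
- Case A: all respondents 0.0007; as written 1.00 (96 vs 48 participants).
- Case B: all respondents 0.020 in favour of prednisone; as written 0.0105 against it (96 vs 36).
- Case C: all respondents 0.0007; as written 0.0003 (96 vs 96).
- Case 1: all respondents 0.19. Case 2: all respondents 0.67; as written 0.21 (72 vs 54). In both, score ≥1 gives 0.020.

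**Bonferroni.** With one test per symptom and 20, 25 or 30 symptoms, 0.05/20 = 0.0025, 0.05/25 = 0.0020 and 0.05/30 = 0.0017. Neither reversal (case 2 or case B) reaches these limits, so each would be a wrong direction and not a significant result.

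**The case against.** The strongest objection is that severity is only half of the planned analysis. The same sentence also compares frequency, and presence in everyone followed by severity among those with the symptom is a recognisable design that fits section 21.1. If a score of 1 or more counts as present, participants who move to 0 are credited in the frequency test. In cases 1 and 2 that test (60% vs 45%, p = 0.020) is more sensitive than the 3-4 comparison in all respondents (p = 0.19 and 0.67).

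Nor is a 0 to 4 scale established for the trial form. Section 21.1 is background on the published index. The trial used an adapted version, to be finalised after patient and provider feedback (section 21.2), and the questionnaires in Appendix 22.4 are not shown. Four severity codes with absence recorded separately would fit both the 4-point label and the SAP split.

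These points stand. A reader might infer that the SAP contains a proven scoring error that erases a treatment effect. The documents do not support that: the meaning of 0 is open, frequency is also tested, and the distortion needs unequal zeros.

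The objection does not rescue the severity test itself. If 0 means absent, or absence is recorded separately, the test is still confined to participants who have the symptom after treatment. If 0 means present but not bothersome and frequency counts presence, frequency could be equal in both arms and neither test would show the benefit in case A. The SAP does not define frequency, and a good frequency result does not correct a severity result reported beside it.

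**Conclusion.** The concern holds as a limited point. As written, the severity comparison leaves score 0 unassigned and conditions on a status that treatment can change, without saying so, in a section described as ITT. It can therefore hide or reverse a real difference in bothersome symptoms. In the assumed cases, 30% vs 22.5% becomes 50% vs 50%, and 33.3% vs 20% becomes 41.7% vs 66.7%. With equal zeros in both arms there is no loss.

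The sizes rest entirely on assumed distributions, and the 120 per arm on full response. It would go too far to read this as a significant false harm, since neither illustrated reversal would survive Bonferroni, or as a threat to the trial's main conclusion. The index is one of four instruments within one of 18 secondary efficacy items (a to r). The primary endpoint is untouched.

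**What to change.** Amend SAP 4(p) before unblinding, so that the denominator is not chosen with the results in view:

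- For each symptom and visit, compare the proportion scoring 3-4 with all others (0-2, with an absent symptom counted as not bothersome), among all participants in each arm who completed the item.
- Keep 1-2 vs 3-4 among those with the symptom as a descriptive table, with the denominators shown.
- Reconcile the response codes in the SAP with protocol section 21.1 and the questionnaire actually used, without presuming that they run from 0 to 4.
- State which response counts as symptom present for the frequency comparison.
- Keep the Bonferroni correction and state its divisor.

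The cost is a few lines of SAP text and a small change to the analysis program. No new data are needed.

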Thirdly, on the condition that multi-group scalar invariance is proven (see above), the QOL measures will be used as one of the outcome measures in the clinical trial comparing the use of prednisone with placebo in patients at high risk of TB-IRIS. Comparison of means (SD) and medians (IQR) of the scores (total and domain scores) obtained by the different tools in the placebo and the intervention group will be done using Wilcoxon rank sum, chi-square and Fisher's exact tests, as appropriate.

Table: Summary of Quality of Life assessments to be performed within the clinical trial

| Instrument | Method | Interviewees |
|---|--|---|
| PROQOL-HIV (including “TB” in the questions, next to “HIV”) | Self-administered questionnaire (or administered by counselor) | All participants at week 0, 4 and 12 visit |
| EQ-5D-3L | Self-administered questionnaire (or administered by counselor) | All participants at week 0, 4 and 12 visit |
| HIV-symptom index (complemented with specific symptoms related to IRIS and steroid side effects) | Self-administered questionnaire (or administered by counselor) | All participants at week 0, 4 and 12 visit |
| Karnofsky score | Score assigned by investigator in discussion with participant | All participants at week 0, 4 and 12 visit |
| Respondent debriefing interviews | In-depth interview conducted by an investigator specifically involved in QoL substudy with assistance of counselor for translation | 10-15 interviews with a random sample of participants |

REFERENCES

2. [name], Lawn SD, Scano F, Maartens G, French MA, Worodria W, Elliott JH, Murdoch D, Wilkinson RJ, Seyler C *et al*: **Tuberculosis-associated immune reconstitution inflammatory syndrome: case definitions for use in resource-limited settings.** *Lancet Infect Dis* 2008, **8**(8):516-523.
3. [name], Wilkinson RJ, Morroni C, Pepper DJ, Rebe K, Rangaka MX, Oni T, Maartens G: **Randomized placebo-controlled trial of prednisone for paradoxical tuberculosis-associated immune reconstitution inflammatory syndrome.** *AIDS* 2010, **24**(15):2381-2390.

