All these narratives were reviewed by an independent TB-IRIS review committee comprised of 3 expert clinicians not active at the clinical site. This review was performed in accordance with PREDART SOP 2016/19 ("PredART trial: Review of suspected TB-IRIS cases by independent endpoint review committee). Individual decisions regarding whether the case fulfilled the INSHI case definition were made, followed by consensus seeking according to the SOP to derive a final committee decision whether the case fulfilled the INSHI case definition for paradoxical TB-IRIS – this will be used as the primary endpoint event for the PredART trial.

The statistical analysis for the primary endpoint will compare the proportion of participants in the prednisone arm who fulfilled the INSHI paradoxical TB-IRIS definition to the proportion in the placebo arm, within 12 weeks from randomization. The analysis will be an intention to treat (ITT) analysis including all 240 participants randomized. A Chi-square test or Fisher exact test (as appropriate) will be used. A p-value of less than 0.05 will be regarded as significant for the primary endpoint analyses, and all other analyses performed. In addition, the relative risk of TB- IRIS will be estimated together with a 95% confidence interval. The primary hypothesis of the study is that the proportion of patients developing paradoxical TB-IRIS within 12 weeks of starting ART, as determined by the INSHI case definition and confirmed by the endpoint review committee, will be lower in patients randomized to prednisone compared to patients randomized to placebo.

In addition, as a secondary analysis, an all-patients-treated approach will be performed excluding those participants who were randomized but never started study medication and/or ART.

4. Analysis of secondary efficacy endpoints

A number of secondary efficacy analyses will be performed, all on the ITT population and the all-patients-treated population:

- a) Comparison of proportion of participants who fulfil at least one INSHI major criterion for diagnosis of paradoxical TB-IRIS in each arm. This will be done using Chi-square test or Fisher exact test (as appropriate).

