- Hyperglycaemia (random glucose > 11.1 mmol/l)

- Hypomania/mania
- Depression
- Acne
- Epigastric pain
- Upper gastro- intestinal bleeding
- Cushingoid features
- New oedema
- Avascular bone necrosis

b) Comparison of laboratory safety bloods done at week 2, 4 and 12: sodium, potassium, creatinine, ALT, alkaline phosphatase, total bilirubin, glucose, haemoglobin, white cell count, neutrophil count, total lymphocyte count and platelets. Comparison of medians will be performed at each time point using the Wilcoxon rank sum test. The proportion of participants who develop an ACTG grade 3 or grade 4 abnormality in these blood tests will also be compared using Chi-square test or Fisher exact test (as appropriate).

c) Comparison of week 12 CD4 count and HIV viral load results. Comparison of medians will be performed using the Wilcoxon rank sum test. Proportion of participants with less than $2 \log_{10}$ drop in HIV viral load from screening to week 12 will be compared using the Chi-square test or Fisher exact test (as appropriate). Where screening viral load was too low to ascertain a $2 \log_{10}$ drop then an undetectable viral load at week 12 will be regarded as successful outcome.

d) Comparison of the proportion of participants who are diagnosed with other infections (AIDS-related, bacterial, fungal and viral) and malignancies (Kaposi's sarcoma) will be compared using Chi-square test or Fisher exact test (as appropriate). These will also be presented with individual listing. The proportion with severe infections (classified as any AIDS-defining (WHO stage 4) infection or invasive bacterial infection) will be compared in a separate analysis.

e) The proportion of participants with any clinical ACTG grade 1, 2, 3 and 4 adverse events (AEs) will be compared using Chi-square test or Fisher exact test (as appropriate). A similar comparison will be made for serious adverse events (SAEs) and adverse drug reactions (ADRs) attributed as definite, probably or possibly due to medication (the relationship between ADRs and medication has been determined by the study doctors and categorized as definitely not, unlikely, possibly, probably or definitely related to any medication).

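### SAP 4(p) Bonferroni-corrects the HIV symptom tests without defining the family or exempting the added steroid side-effect items, so on the plain reading these items face a bar at least 20 times stricter than the corticosteroid events in SAP 5

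*Supplement*

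**What the plan says.** **The instrument.** Protocol version 1.4, section 21.2, item 2: "The 20-item HIV symptom index will be complemented with symptoms targeted to patients with IRIS and side effects of steroids". The summary table closing section 21.2 gives the extended index to all participants at weeks 0, 4 and 12. Section 21.1 explains why: the original list has no items aimed at steroid side effects or TB-IRIS. The number of added items is not given.

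**The tests.** SAP 4(p) plans a "Comparison of quality of life assessment between the two arms at week 4 and at week 12". For this instrument: "For the HIV-symptom index the frequency (proportion) and the severity of each symptom (score 1-2 vs score 3-4) will be compared using the Chi-square test". The correction follows: "Because of multiplicity, Bonferroni correction will be applied in the analysis of HIV symptoms". No divisor is stated, nothing says whether measures and visits are pooled, and the added items are not mentioned. Bonferroni appears nowhere else in the SAP.

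**The rule elsewhere.** SAP section 3: "A p-value of less than 0.05 will be regarded as significant for the primary endpoint analyses, and all other analyses performed". SAP 5(a) tests the corticosteroid events together and singly; the sentence on single events, which ends by announcing a between-arm comparison, begins "The proportion of participants in each group who develop individual potential corticosteroid-associated adverse events within 4 weeks and within 12 weeks of randomization will also". SAP 5(e) treats graded events the same way, with the exact test as the alternative: "The proportion of participants with any clinical ACTG grade 1, 2, 3 and 4 adverse events (AEs) will be compared using Chi-square test or Fisher". No multiplicity correction is stated anywhere in SAP 5.

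**The concern.** Family-wise error control guards against false claims of benefit when many outcomes are tested. For harms the priorities reverse: the costlier mistake is usually to miss a real excess. The steroid items were added to pick up what prednisone does to patients, yet they sit inside a quality-of-life analysis that carries the SAP's only multiplicity penalty. The same between-arm contrast could be significant in the SAP 5 tables and non-significant under 4(p), purely because of where it is filed.

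Safety is one of the four objectives in protocol 4.1, and the primary objective in 3.1 is worded to require no excess of adverse events. For items of this kind, an estimate with its interval tells the reader more than a heavily corrected test.

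**Working it through.** **1. The plan's own calculation.** The documents give no corrected threshold, so the only figure to reproduce is the sample size in protocol 14.1: 35% vs 17.5%, two-sided 5%, 80% power. With mean proportion 0.2625:

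n' = [1.960·√(2 × 0.2625 × 0.7375) + 0.842·√(0.35 × 0.65 + 0.175 × 0.825)]² / 0.175² = 98.0

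With continuity correction, n = (n'/4)·[1 + √(1 + 4/(n' × 0.175))]² = 109.2, so 110 per arm, as stated. I use 110 per arm below; it is close to 120 per arm less the assumed 10% loss (108).

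**2. Corrected threshold.** Bonferroni uses 0.05/m. The list has 20 items plus an unstated number of additions. Lengths of 25 and 30 are my assumptions.

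| Family | m | Threshold | Times stricter than 0.05 |
|---|---|---|---|
| Original 20 items, one measure, one visit | 20 | 0.0025 | 20 |
| 25 items, one measure, one visit | 25 | 0.0020 | 25 |
| 30 items, one measure, one visit | 30 | 0.0017 | 30 |
| 25 items × 2 measures (or 2 visits) | 50 | 0.0010 | 50 |
| 25 items × 2 measures × 2 visits | 100 | 0.0005 | 100 |

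If the extended list is one family, m exceeds 20, so the factor of 20 is a lower bound. The last two rows need pooling that the SAP does not state.

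**3. Power for one side-effect item.** Assumed rates are 15% vs 30%, 110 per arm, mean 0.225.

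- SE under the null: √(2 × 0.225 × 0.775/110) = 0.0563
- SE under the alternative: √[(0.15 × 0.85 + 0.30 × 0.70)/110] = 0.0554
- Power = Φ[(0.15 − z × 0.0563)/0.0554]
- At 0.05, z = 1.960: Φ(0.716) = 0.763
- At 0.05/25, z = 3.090: Φ(−0.433) = 0.332
- At 0.05/100, z = 3.481: Φ(−0.830) = 0.203

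Other assumed rates at 110 per arm, uncorrected and then with 25 tests: 10% vs 25%, 0.84 and 0.43; 20% vs 35%, 0.71 and 0.27.

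**4. The same result under both rules.** Take a hypothetical 36/120 vs 18/120. Pooled proportion 0.225, SE √(2 × 0.225 × 0.775/120) = 0.0539, z = 0.15/0.0539 = 2.78, chi-square 7.74, p = 0.005. This passes at 0.05 and fails at 0.0025. The difference is 15 points, with 95% CI 0.15 ± 1.96 × √[(0.30 × 0.70 + 0.15 × 0.85)/120], that is 4.6 to 25.4 points.

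**5. Holm against Bonferroni.** Simulation with 25 correlated symptoms (latent correlation 0.3), 110 per arm, average power per affected symptom:

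| Affected symptoms | Rates | Bonferroni | Holm | Gain (points) |
|---|---|---|---|---|
| 5 | 20% vs 35% | 0.285 | 0.289 | 0.4 |
| 10 | 20% vs 35% | 0.282 | 0.294 | 1.2 |
| 15 | 20% vs 35% | 0.269 | 0.289 | 2.0 |
| 15 | 20% vs 45% | 0.823 | 0.869 | 4.6 |

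**The case against.** **The harms are tested elsewhere.** This largely stands. SAP 5(a) tests acne, epigastric pain, depression, mania, Cushingoid features and oedema at 0.05, within 4 and 12 weeks, and SAP 5(e) adds graded adverse events, serious adverse events and drug reactions. A reader might infer that patient-reported prednisone harms as a whole are held to the stricter bar, or that this index is the only patient-reported information on them. The documents do not support either. Symptoms told to the study doctor feed the adverse event record, and the EQ-5D-3L pain/discomfort and anxiety/depression domains are compared uncorrected in 4(p) itself. The overlap is incomplete, though: under protocol 11.5, depression and mania need a psychiatrist's diagnosis, and Cushingoid features rest on the investigator's opinion.

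**The family is inferred.** This stands. HIV symptoms could mean the original 20 items only, or the correction could be made within sub-families. The SAP says neither, and that silence is part of the defect. A hundred-test family is only one possible reading.

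**Correcting a long quality-of-life list is defensible.** True for benefit. The protocol files the index under secondary efficacy, and 25 to 100 uncorrected tests would give about 1 to 5 chance positives under the null (25 × 0.05 = 1.25; 100 × 0.05 = 5). That supports correcting the HIV and IRIS symptoms, but is weaker for items added to detect side effects.

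**Bonferroni hides nothing.** It changes the significance label and leaves the observed proportions alone. A reader might infer that a non-significant item would be reported as evidence of tolerability; no passage says so.

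**Holm is a refinement.** Agreed: Bonferroni is valid and the gain is small.

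**Conclusion.** The point holds within limits. On the plain reading of SAP 4(p), the added steroid side-effect items are tested at 0.0025 or lower, at least 20 times stricter than the 0.05 used for the corticosteroid events in SAP 5. That bound assumes the extended list is treated as one family.

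The loss concerns this instrument's items only. For an assumed 15% vs 30% with 110 per arm, power falls from 76% to about 33% with 25 corrected tests. The direction is firm; the amount depends on the unstated list length and on symptom rates the documents do not give. It is an inconsistency in how harms are judged, cheap to put right, and it leaves the primary analysis and SAP 5 untouched.

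**What to change.** Amend SAP 4(p) as follows.

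1. State the corrected family: which symptoms, and whether the two measures and two visits are pooled.
2. Take the added steroid side-effect items out of it. Report them alongside the safety results as between-arm differences with unadjusted 95% confidence intervals. Name the analysis population, because SAP 4 uses both the intention-to-treat and all-patients-treated sets while SAP 5 uses only the latter.
3. For the remaining HIV and IRIS symptoms, replace Bonferroni with Holm's step-down procedure. It controls the same family-wise error without further assumptions and is never less powerful.

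**Cost.** A few sentences and no new data. Some chance excesses will appear, as SAP 5 already accepts for its other harms. If five steroid items were added (an assumption), 5 × 2 measures × 2 visits = 20 intervals, of which 20 × 0.05 = 1 would be expected to exclude zero by chance.

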14.1. Sample size calculation

Assuming 35% cumulative incidence of TB-IRIS in the placebo arm and a 50% reduction in TB-IRIS in the corticosteroid arm (ie. to 17.5%) and requiring 80% power to test for the difference in TB-IRIS incidence at a two-sided significance level of 5%, the sample size required would be 110 in each arm. We will aim to recruit 240 patients assuming loss to follow-up of 10%. The estimate of 35% incidence of TB-IRIS in the placebo arm corresponds to the findings of Blanc et al (110/332 (33%) of participants who started ART in the early arm in this trial had TB-IRIS events (32)) and a study we conducted at Brooklyn Chest TB Hospital in Cape Town (42% IRIS incidence [47]) and reflects that these will be patients at high risk for TB-IRIS due to low CD4 counts and short interval between TB treatment and ART start. Lawn and colleagues demonstrated in a retrospective study conducted in Cape Town that low CD4 count and shorter interval between TB treatment and ART initiation were the strongest predictors of TB-IRIS. In their study 70% of patients with a CD4 count < 100/μl who started ART within 30 days of TB treatment developed TB-IRIS [48].

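### SAP 4(p) tests the HIV symptom index only symptom by symptom with Bonferroni and compares no summary score, so a modest reduction spread over many symptoms is much less likely to be detected on this instrument

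*Supplement*

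**What the plan says.** SAP section 4(p) covers "Comparison of quality of life assessment between the two arms at week 4 and at week 12". For the HIV symptom index it states that "the frequency (proportion) and the severity of each symptom (score 1-2 vs score 3-4) will be compared using the Chi-square test", followed by "Because of multiplicity, Bonferroni correction will be applied in the analysis of HIV symptoms". It names no total, symptom count or global test, and it does not say how many tests the correction covers. SAP section 3 sets the general level: "A p-value of less than 0.05 will be regarded as significant for the primary endpoint analyses, and all other analyses performed".

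The same paragraph gives other instruments a summary measure with no multiplicity correction: PROQOL-HIV domain scores, the EQ visual analogue scale and the Karnofsky score.

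Protocol 1.4 section 21.2 plans the arm comparison differently: "Comparison of means (SD) and medians (IQR) of the scores (total and domain scores) obtained by the different tools", and its table lists the HIV symptom index among those tools. That comparison is made only "on the condition that multi-group scalar invariance is proven". On the length of the index the protocol says: "The 20-item HIV symptom index will be complemented with symptoms targeted to patients with IRIS and side effects of steroids".

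**The concern.** The protocol's plan for the tools includes total scores, and the SAP has none for this index. The SAP neither invokes the invariance condition nor explains the omission. What remains is a family of at least 20 symptoms, two measures per symptom and two visits, each test at a very small level.

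A broad, modest improvement is a plausible pattern here. The investigators' earlier treatment trial, described in protocol section 3.3, reported faster symptom improvement on prednisone. Separate tests with a Bonferroni threshold are poorly suited to such a pattern, because no single symptom need change much. At stake is whether this tool can show a general change in symptom burden, which falls under secondary endpoint 8 of protocol section 6.2.

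**Working it through.** **Inputs from the documents.** At least 20 symptoms (protocol 21.1 and 21.2); two measures per symptom, two visits and Bonferroni (SAP 4(p)); alpha 0.05 (SAP 3); 240 patients randomised 1:1 with 10% loss allowed (protocol 14.1), so 240 × 0.9 / 2 = 108 per arm.

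**Inputs that are assumptions.** Symptom prevalence, size of effect and correlation between symptoms. The documents give none of these.

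**The plan's own figure.** The documents give no power for the symptom index. The trial's sample size does reproduce: 35% vs 17.5%, two-sided 5%, 80% power gives 99 per arm without and 110 with continuity correction. The protocol states 110.

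**Bonferroni level.** The family is not stated, so there are three candidates:
- 20 tests: 0.05/20 = 0.0025
- 20 × 2 measures = 40 tests: 0.05/40 = 0.00125
- 40 × 2 visits = 80 tests: 0.05/80 = 0.000625

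**Power for one given symptom.** With p̄ = (p1 + p2)/2, power = Φ{[|p1 − p2|√n − z(1−α/2)·√(2p̄(1−p̄))] / √(p1(1−p1) + p2(1−p2))}. For a fall from 40% to 30% with n = 108, this is 34% at 0.05 and 6.8%, 4.5% and 2.9% at the three levels above. Reaching 80% would need 679, 752 and 825 per arm.

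**General reduction, first model.** Simulation: 20 present/absent symptoms, one common latent factor, correlation 0.3, 108 per arm, one visit, chi-square per symptom at 0.05/40, and Wilcoxon on the symptom count.

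| Scenario | Any symptom significant | Count at 0.05 | Count at 0.0125 |
|---|---|---|---|
| All 20 symptoms, 30% vs 22% | about 33% (33–36% over repeated runs) | about 80% (80–83%) | 62% (62–66%) |
| All 20 symptoms, 30% vs 20% | 57–58% | 96% | – |
| 4 of 20 symptoms, 30% vs 15% | 66–69% | 16–18% | – |

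The 0.0125 column is 0.05/4, for two summaries at two visits sharing alpha. The per-symptom column simulates only the 20 frequency tests while paying for 40. Adding severity tests, with an assumed threshold and all patients in the denominator, raises the first entry to about 43%.

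**General reduction, second model.** Items scored 0 to 4, prevalence 20–60% (mean 40%), the same latent shift on every item. Ranges run over correlation 0.5 to 0.1 and, for the per-symptom tests, over the three families. The total is tested at one visit at 0.05.

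| Fall at a 40% symptom | Any symptom significant | Total score |
|---|---|---|
| 5 points | 11–19% | 24–62% |
| 7.5 points | 22–43% | 47–95% |
| 10 points | 43–68% | 74–99% |
| 15 points | 85–99% | 98–100% |

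For a general effect the total is the more powerful test throughout. The gap is wide for small and moderate effects and nearly closes at 15 points.

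**The case against.** Four arguments on the other side have weight.

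- **The protocol did not promise a symptom-index total.** A reader might infer this from section 21.2, but the text does not support it. The comparison covers the tools in general, depends on scalar invariance, and names no total for this index. What stands is that the SAP leaves the summary out and does not cite the condition as the reason.
- **A general reduction would not usually be missed at every size.** That inference is tempting, but it holds only for small effects. With a 10-point fall no symptom is significant in 32–57% of trials, and with a 15-point fall in only 1–15%.
- **The per-symptom tests can be the better choice.** Protocol section 3.7 hypothesises fewer and milder TB-IRIS events, which could concentrate the effect in a few symptoms. In the 4-of-20 scenario the ranking reverses (66–69% vs 16–18%). Section 21.1 also introduces the index as a symptom list that helps explain differences in quality of life, and benefit and steroid harm could cancel in a sum. This argument stands: a total should not replace the per-symptom tests, and making it the lead analysis is debatable.
- **General benefit can appear elsewhere.** PROQOL-HIV domains, the EQ visual analogue scale and Karnofsky are compared without correction. A reader might also fear that a null table would be reported as no effect on symptoms, but the SAP contains no such rule. The loss is confined to this one tool.

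None of these explains why the index has no summary comparison at all, or why the size of the Bonferroni family is left open.

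**Conclusion.** The point holds in a limited form. SAP 4(p) gives the HIV symptom index no summary comparison, does not carry over the protocol's conditional plan, and gives no reason. For a small to moderate reduction spread over many symptoms, detection on this tool drops substantially: about 33% (about 43% with severity tests counted) against about 80%, or 62% with alpha shared over four total tests. These figures rest on assumed prevalences of 30% vs 22%, correlation 0.3, an equal effect on all 20 symptoms and 108 per arm. For large general effects the difference is small, and for concentrated effects the per-symptom tests win, so the two analyses complement each other. The matter concerns one of several tools within one of eighteen secondary efficacy items and has no bearing on the primary conclusion.

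**What to change.** Before unblinding, amend SAP 4(p) as follows.

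1. Add a Wilcoxon comparison of one pre-specified summary of the index, either the symptom count or the summed bother score, at weeks 4 and 12. Choosing one rather than both limits the sharing of alpha.
2. Report separate subtotals for the added TB-IRIS items and the added steroid-side-effect items, so that benefit and harm do not cancel.
3. Keep the per-symptom tests alongside, and replace Bonferroni with Holm over a stated family of tests. Holm gives the same error control and is never less powerful. Its first step equals Bonferroni, so it does not raise the chance of finding at least one significant symptom; the summary has to do that.
4. State the scoring. Protocol 21.1 describes a four-point scale but anchors it at 0 and 4, and the SAP does not say whether patients without a symptom enter the denominator of the severity comparison.

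The cost is SAP wording and a sum over data already collected. The downsides are a few more secondary tests, and that a total does not show which symptom changed, which is why the per-symptom table stays.
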